#### Multiple Comparisons/Multiplicity

Multiplicity will be adjusted for in the primary effectiveness subgroup analysis and is further detailed in Section 2.4.3.2.

	Title 43USTT1904 Statistical analysis plan - Tear Trough	Doc id
GALDERMA 657, 1981		MA-42205

2022-08-17 17:26

For all secondary effectiveness endpoints, no correction for multiplicity will be done; p-values obtained for any endpoint other than the primary will only be provided for ease of interpretation of the results.

#### 2.2 Analysis Populations

There will be three analysis populations defined for this study:

- Modified Intention-to-treat (mITT) Population Includes all subjects who are randomized
  and will be analyzed according to the randomization scheme; subjects with a GIHS Month 3
  assessment via a remote visit (i.e. remote office visit and/or GIHS assessment done
  remotely) will be excluded
- Intention-to-treat (ITT) Population Includes all subjects who are randomized at baseline and will be analyzed according to the randomization scheme determined at baseline
- Per protocol (PP) Population Includes all subjects in mITT who complete 3 months after baseline visit without any deviations considered to have substantial impact on the primary effectiveness
- Safety Population Includes all subjects who are treated with Restylane-L or randomized to the control group, and will be analyzed according to as-treated principle

#### 2.3 Study subjects

#### 2.3.1 Subject disposition

The disposition of subjects will be presented by treatment group (Restylane-L, No Treatment) and in total, including number of subjects that were:

- Screened, including screen failures
- Enrolled
- Randomized
- Study Completers
- Early withdrawals/discontinuations
- Restylane-L group (Needle or Cannula) or No Treatment group
- ITT population
- PP population
- Safety Population

Specifically, the number and percentage of subjects in each of the specified categories above will be presented. The discontinuation reason as specified on the electronic case report forms (eCRFs) will also be summarized by number and percent.

All withdrawn/discontinued subjects and inclusion/exclusion data will be presented by subject in data listings.

#### 2.3.2 Protocol deviations

Subjects with protocol deviations will be listed individually, including subject number and observed deviation. The following are considered protocol deviations for this study:

- SAE Reporting
- Study Product Use

Doc id 43USTT1904 Statistical analysis plan - Tear Trough GALDERMA MA-42205

Print date:

2022-08-17 17:26

- Missed Procedure
- Eligibility
- Photography
- Informed Consent
- Missed Visit
- Prohibited Medication or Procedure
- Out of Window Visit
- Remote Visit, all assessments done
- Remote Visit, all assessments not done

Depending on the seriousness of the deviation, a subject might be excluded from the PP population, which shall be documented in a listing prior to database lock.

For this study, the protocol deviations that will exclude subjects from PP are identified (but not limited to) in Table 1 below. Deviations from the SAP will be documented in the CSR.

Table 1. Protocol deviations

	Deviation
÷	Any subject that conducts their Month 3 visit significantly out-of-window
*	Any subject that misses the primary endpoint visit (Month 3)
÷	Any subject not treated according to the assigned treatment
*	Any subject that does not complete the GIHS at the primary endpoint visit (Month 3)
÷	Any subject that do not have Grade 2 or 3 on the Blinded Evaluator GIHS at baseline
*	Any subject with more than 1 grade difference in Blinded Evaluator GIHS between the left and right side at baseline
*	Any subject with prohibited concomitant treatments/procedures prior to Month 3 visit considered to have a substantial impact on the primary effectiveness outcome.
*	Any subject with a prohibited medical history, unstable medical history, or medical history that worsens prior to Month 3 visit considered to have a substantial impact on the primary effectiveness outcome

#### 2.3.2.1 Out of Window visit duration

When a subject performs a planned study visit outside of the protocol-specified visit windows (Appendix G), the subject has an out of window study visit, which is considered a type of protocol deviation for this study. Knowing a subject's Screening visit (Visit 1a) and Baseline visit (Visit 2) and using the protocol-specified visit windowing, one can calculate a subject's target study visit window date range for each planned study visit. Then, by comparing a subject's actual study visit date to the target study visit window date range, one can calculate the days over/under the actual study visit was in relation to the target study visit date, or study visit out of window duration.

	Title 43USTT1904 Statistical analysis plan - Tear Trough	Doc id
GALDERMA 657, 1981		MA-42205

2022-08-17 17:26

The duration, in days, a study visit is out of window will be summarized by treatment group, overall, and by visit. Out of window visit durations will also be presented by site as well. Duration will be split into the following below categories. Duration categories will include both days before and days after the target planned visit date.

- +/- 1-2 days
- +/- 3-7 days
- +/- 8-20 days
- +/- 21 or more days

The number and percentage of subjects within each out of window duration category will be presented descriptively. For the overall analysis, percentages will be calculated using the number of subjects with an out of window visit at the respective visit as the denominator; for the by site analysis, percentages will be calculated using the number of subjects at the respective site as the denominator.

#### 2.3.3 Demographic characteristics

Demographic assessments for this study include:

- Age (years)
  - Age groups using a median split
- Height (in)
- Weight (lbs.)
- BMI (kg/m²)
  - BMI groups using a median split
- Gender (Male, Female)
- Ethnicity (Hispanic or Latino, Not Hispanic or Latino)
- Race (White, Black or African American, Asian, American Indian or Alaska Native, Native Hawaiian or Other Pacific Islander, Other)
- FST score (I, II, III, IV, V, VI)
- Blinded Evaluator GIHS, both sides of face (0, 1, 2, 3)

[figure not shown]
The demographic and baseline characteristic analyses will be presented by treatment group and overall and will be based on the ITT population using the appropriate descriptive statistics for continuous and categorical variables. Age, height, weight, and BMI will be analyzed as continuous variables. Gender, race, ethnicity, FST score and GIHS scores will be analyzed as categorical variables.

Demographics and baseline characteristics will be presented by subject in a data listing.

#### 2.3.4 Medical and surgical history

All summaries will be done by treatment group based on the ITT population. History of relevant or clinically significant surgical events and medical conditions, including any prior dermatological/cosmetic procedures or implants, will be collected. Medical History will be coded according to MedDRA; the version used will be noted as a footnote in the tables and listings.

The number and percent of subjects reporting medical history, and the number of events will be summarized by system organ class (SOC) and preferred term (PT). System organ class and PTs will be presented in descending frequency first, and then alphabetically if there are ties. Each subject

2022-08-17 17:26

will contribute at most one count per summarization category. In other words, if a subject has more than one medical history event with same PT, the subject will be counted only once for that PT. Similarly, if a subject has more than one medical history event for a SOC, the subject will be counted only once in that SOC and PT. For the event level analyses, counts of each respective event will be presented.

Prior dermatological/cosmetic procedures or implants will also be presented and will follow the same methods specified above.

Medical history information and prior dermatological/cosmetic procedures or implants will be presented by subject in a data listing.

#### 2.3.5 Concomitant medication/procedures

All summaries will be done by treatment group based on the Safety Population. Concomitant medications/therapies/procedures for this study are defined as any existing medications/ therapies/ procedures ongoing at the time of the screening visit, any changes to existing medications/ therapies (such as dose or formulation) during the course of the study, or any new medications/therapies received by the subject since the screening visit. Concomitant medications/therapies will be coded using the World Health Organization (WHO) Drug Dictionary; concomitant procedures will be coded according to MedDRA. The versions used for the coding will be noted as a footnote in the tables and listings.

The number and percent of subjects reporting concomitant medications/therapies, and number of drugs, will be summarized by the WHO Drug Dictionary Anatomical Therapeutic Chemical 3rd level (ATC-3) and the preferred name. If the 3rd level term is not available, the next available level (e.g., ATC-2) will be used. In addition, the number and percent of subjects reporting a concomitant medication/therapy, and the number of drugs will be summarized by reason. Concomitant medications that started due to an AE will be summarized separately.

ATC-3 and preferred name will be presented in descending frequency first, and then alphabetically if there are ties. Each subject will contribute at most one count per summarization category. In other words, if a subject has more than one medication with same preferred name, the subject will be counted only once for that preferred name. Similarly, if a subject has more than one medication for an ATC-3 level, the subject will be counted only once in that ATC-3 level and preferred name. For the number of drugs, counts of each respective medication will be presented.

Concomitant procedures will also be presented, and will follow the same methods specified for medical history (Section 2.3.4).

Concomitant medications/procedures will be presented by subject in a data listing.

#### 2.4 Effectiveness analysis

GALDERMA

Table
43USTT1904 Statistical analysis plan - Tear Trough

MA-42205

Print date:

2022-08-17 17:26

CCI		

#### 2.4.1 Datasets analyzed

The mITT population will be used for the primary effectiveness analysis. All secondary effectiveness analyses will be based on the ITT population.

#### 2.4.2 Handling of missing data

In general, the number of missing values will be summarized and reported as appropriate in all outputs. The primary analysis will be performed using MI as the primary imputation method. The MI methods are detailed in Appendix H.

CCI		

GALDERMA

Title
43USTT1904 Statistical analysis plan - Tear Trough

MA-42205

Print date:

2022-08-17 17:26

CCI		

#### 2.4.3 Primary effectiveness analysis

The primary effectiveness analysis will be done using the mITT Population. To evaluate the effectiveness of Restylane-L versus no-treatment control in the correction of Infraorbital Hollows, the GIHS responder rates (defined in Section 1.3.1) at Month 3 after baseline will be compared using the CMH test stratified by injection tool at the 5% significance level (2-sided).

The null hypothesis will be that there is no relationship between GIHS responder rate and treatment group (i.e. the responder rate is the same in both Restylane-L and no treatment groups). The alternative hypothesis will be that there is a relationship between responder rate and treatment group (i.e. the responder rate is different in the two groups). For a significant result, the two-sided p-value of the comparison of GIHS responder rates between the treated and untreated subjects at Month 3 using the CMH test needs to be smaller than 0.05.

The estimates of the GIHS responder rates in each treatment group will be presented as well as the difference in responder rates (Restylane-L responder rate – No Treatment responder rate). Corresponding 95% CI for the treatment group GIHS responder rates and the difference in responder rates along with the p-value for the difference will also be presented. The normal approximation (Wald) method will be used to calculate the 95% CI for the individual treatment group GIHS responder rates as well as the 95% CI for the difference in responder rates.

Effective date: 2021-12-1713:25

Version: 3.0

Title 43USTT1904 Statistical analysis plan - Tear Trough

Doc id

[figure not shown]
Print date:

MA-42205

2022-08-17 17:26

Effective

Effective

Print date:

[figure not shown]
2022-08-17 17:26

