5.2 Inclusion criteria

The subjects must meet all the following criteria to be eligible for the study:

1. Subject is willing to comply with the requirements of the study including being photographed, following post-treatment care instructions, completing the diary, attending all study visits and providing a signed written informed consent.
2. Moderate or severe (Grade 2 or 3 on the GIHS) infraorbital hollows with no more than one grade difference between the left and right side at baseline as assessed by the blinded evaluator.
3. Visual function assessment tests without findings according to treating investigator.
4. Males or non-pregnant, non-breastfeeding females, over the age of 21.
5. Subject is willing to abstain from any other facial plastic surgical or cosmetic procedure(s) during the duration of the study (e.g. laser or chemical resurfacing, needling, facelift, radiofrequency).
6. Intent to undergo correction of both orbital hollows.

Inclusion criteria 7 - 8 apply to female subjects only

7. If the subject is a female of childbearing potential, she agrees to use an acceptable form of effective birth control for the duration of the study and is willing to take a urine pregnancy test (UPT) at the screening/enrollment visit and prior to treatment. Acceptable forms of effective birth control include:
 - a) Barrier methods of contraception: Condom or Occlusive cap (diaphragm or cervical caps) with spermicidal foam/gel/film/cream/suppository.
 - b) Bilateral tubal ligation.
 - c) Combined oral contraceptives (estrogens and progesterone), implanted or injectable contraceptives on a stable dose for at least 28 days prior to Day 1.
 - d) Hormonal or copper intra uterine device (IUD) inserted at least 28 days prior to Day 1.
 - e) Vasectomized partner (in monogamous relationship) for at least 3 months prior to screening.
 - f) Strict abstinence (at least one month prior to baseline and agrees to continue for the duration of the study or use acceptable form or birth control).

	Title 43USTT1904 CSP Infraorbital Hollows	Doc id MA-40833
--	---	---------------------------

8. Negative urine pregnancy test for females of childbearing potential at screening and all injection visits.

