10.4 Effectiveness analysis

10.4.1 Primary effectiveness analysis:

Responder rate based on the GIHS as assessed live by the Blinded Evaluator at month 3 after baseline will be the primary effectiveness endpoint. A responder will be defined as a subject with at least 1 point improvement from baseline on both sides of the face concurrently. For a significant result, the two-sided p-value of the comparison of responder rates between the treated and untreated subjects at month 3, using the Cochran-Mantel-Haenszel (CMH) test stratified by injection tool, needs to be smaller than 0.05.

The null hypothesis will be that there is no relationship between responder rate and treatment group (i.e. the responder rate is the same in both groups). The alternative hypothesis will be that there is a relationship between responder rate and treatment group (i.e. the responder rate is different in the two groups).

	Title 43USTT1904 CSP Infraorbital Hollows	Doc id MA-40833
--	---	---------------------------

The estimates of the responder rate in each treatment group will be presented as well as the difference in responder rates. Corresponding confidence intervals for responder rates and the difference in responder rates along with the p-value for the difference will also be presented.

CCI

10.4.2 Secondary effectiveness analysis:

Responder rates (defined as at least 1 point improvement from baseline on both sides of the face concurrently) based on the GIHS as assessed by the Blinded Evaluator at month 6, 9, and 12 after baseline and at 3 and 6 months after optional treatment will be analyzed in the same way as the primary effectiveness endpoint. No correction for multiplicity will be done; p-values obtained for any endpoint other than the primary will only be provided for ease of interpretation of the results.

All other secondary effectiveness analyses will be done descriptively as appropriate.

10.5 **Safety analysis**

Number and percentage of subjects reporting each pre-defined, expected, post-treatment symptoms, as collected in the 28 days diary, will be presented in total and by maximum severity. Number of days with the event will be presented by treatment group and category: 1, 2-7, 8-13, and 14-28.

All AEs will be coded according to MedDRA and summarized by system organ class (SOC), preferred term (PT) and treatment.

A summary of all AEs will be provided, which will include:

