10.11 Sample size

Due to the public health emergency related to the COVID-19 pandemic during 2020, steps have been taken to ensure patient and practitioner safety in alignment with FDA Guidance dated May 11, 2020 (Guidance on Conduct of Clinical Trials of Medical Products during COVID-19 Public Health Emergency). Most notably, in partnership with clinical sites and the IRB, optional remote assessment procedures for efficacy and safety endpoints has been implemented to ensure safety and respect localized and elective restrictions. Therefore, the sample size has been increased during the conduct of the study to ensure a sufficient number of subjects in the mITT population used in the assessment of the primary effectiveness endpoint.

The study was initially planned to enroll a total sample size of approximately 238 subjects; approximately 204 randomized to treatment with *Restylane-L* (~102 injected using needle, and ~102 injected using cannula) and approximately 34 randomized to no treatment.

Based on information on missing data and the number of remote visits performed at study sites so far, the study is now planned to enroll approximately 329 subjects; approximately 282 will be randomized to treatment with *Restylane-L* (~146 will be injected using needle, and ~136 will be injected using cannula) and approximately 47 will be randomized to no treatment in order to achieve the required number of mITT subjects in each stratum.

CCI

	Title 43USTT1904 CSP Infraorbital Hollows	Doc id MA-40833
--	---	---------------------------

Effective date: 2021-12-15 20:29

CCI

11. Protection of personal data

All processing of personal data must be carried out in accordance with national legislation concerning the protection of personal data. The Institution and the Investigator are responsible for complying with all requirements pursuant to national legislation in which the Institution and the Investigator are located. The Sponsor will ensure that all requirements for data processing are fulfilled.

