#### 2.7 Determination of Sample Size

Due to the public health emergency related to the COVID-19 pandemic during 2020, steps have been taken to ensure patient and practitioner safety in alignment with FDA Guidance dated May 11, 2020 (Guidance on Conduct of Clinical Trials of Medical Products during COVID-19 Public Health Emergency). Most notably, in partnership with clinical sites and the IRB, optional remote assessment procedures for efficacy and safety endpoints has been implemented to ensure safety and respect localized and elective restrictions. Therefore, the sample size has been increased during the conduct of the study to ensure a sufficient number of subjects in the mITT population used in the assessment of the primary effectiveness endpoint.

The study was initially planned to enroll a total sample size of approximately 238 subjects; approximately 204 randomized to treatment with Restylane-L ( $\sim$ 102 injected using needle, and  $\sim$ 102 injected using cannula) and approximately 34 randomized to no treatment.

Based on information on missing data and the number of remote visits performed at study sites so far, the study is now planned to enroll approximately 329 subjects; approximately 282 will be randomized to treatment with Restylane-L (~146 will be injected using needle, and ~136 will be injected using cannula) and approximately 47 will be randomized to no treatment in order to achieve the required number of mITT subjects in each stratum.

2022-08-17 17:26

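### The visible primary analysis does not adjust for baseline GIHS grade, which costs some precision and leaves the estimate open to a shift of a few points under chance imbalance

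*SAP*

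**What the plan says.** SAP 2.4.3 states that the Month 3 responder rates "will be compared using the CMH test stratified by injection tool at the 5% significance level (2-sided"). Protocol 10.4.1 agrees: the p-value of the CMH "test stratified by injection tool, needs to be smaller than 0.05". SAP 2.4.3 gives normal-approximation (Wald) intervals for the arm rates and for their difference, and mentions no stratification of either.

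Protocol 5.2 admits subjects with "Moderate or severe (Grade 2 or 3 on the GIHS) infraorbital hollows", as rated by the Blinded Evaluator. Response is an improvement of at least one grade from the subject's own baseline on both sides (SAP 1.4.1). SAP 2.3.3 lists "Blinded Evaluator GIHS, both sides of face (0, 1, 2, 3") among the characteristics tabulated by treatment group.

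Randomisation (Protocol 4.4.1, SAP 1.1.2) is stratified by Fitzpatrick skin type group, then by site (types I-III) or by tool (types IV and V-VI). Baseline grade is not a stratum.

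On size, SAP 2.7 says "the study is now planned to enroll approximately 329 subjects; approximately 282 will be" randomised to Restylane-L and "approximately 47 will be randomized to no treatment in order to achieve the required number of mITT subjects in each stratum".

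**The concern.** The endpoint is a change on a four-point scale that subjects enter at its top two grades. Grade 3 is the ceiling, so rating error at grade 3 can only look like improvement, whereas at grade 2 it can go either way. Response may therefore depend on baseline grade, with or without treatment. Defining response as change from baseline does not remove that dependence.

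With about 47 controls, the share of severe subjects can differ noticeably between arms by chance. If grade is prognostic, two things follow. Variance that a recorded baseline value could explain stays in the interval. A visible imbalance in the baseline table also carries through to the reported difference, and the visible text gives no pre-specified adjusted estimate to set beside it.

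**Working it through.** **1. The plan's own figures.** Treated subjects by tool: "146 will be injected using needle, and ~136 will be injected using cannula". 146 + 136 = 282, and 282 + 47 = 329. For the initial plan, 204 + 34 = 238. Both give 6:1 (282/47 = 204/34 = 6). The visible text gives no responder rates, power or attrition, and Protocol synopsis (Sample size) says there are no existing data on this scale. Everything below therefore rests on assumptions: half the subjects severe, several pairs of response rates, and a gradient g (difference in response rate between baseline grades, equal in both arms) of 0 to 30 points.

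**2. Chance imbalance in the share severe.** SD = sqrt(0.25 x (1/n1 + 1/n0)).

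| Treated vs control | SD (points) | 95% range | P(imbalance > 10 points) |
|---|---|---|---|
| 282 vs 47 | 7.9 | ±15.4 | 20% |
| 204 vs 34 | 9.3 | ±18.2 | 28% |

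The second row uses the initial control number ("approximately 34 randomized to no treatment") as a lower case, because exclusion of remote Month 3 assessments makes the mITT set smaller than 47 by an amount the visible text does not state.

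**3. Shift in the crude difference.** Shift = g x imbalance. At exactly 10 points of imbalance it is 1, 2 or 3 points for g = 10, 20 or 30. Averaged over all imbalances above 10 points (mean about 13.7 by the normal formula) it is about 1.4, 2.7 and 4.1 points. At the 95% limit of 15.4 points it is 1.5, 3.1 and 4.6 points. The grade-stratified estimate shifts by about zero.

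**4. Variance that grade explains.** With half the subjects severe, the crude variance is V = p1(1-p1)/282 + p0(1-p0)/47. The part due to grade is g² x 0.25 x (1/282 + 1/47) = g² x 0.006206.

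| Treated vs control | V | SE (points) | g = 10 | g = 20 | g = 30 |
|---|---|---|---|---|---|
| 80% vs 15% | 0.00328 | 5.7 | 1.9% | 7.6% | 17.0% |
| 70% vs 20% | 0.00415 | 6.4 | 1.5% | 6.0% | 13.5% |
| 60% vs 30% | 0.00532 | 7.3 | 1.2% | 4.7% | 10.5% |
| 50% vs 30% | 0.00535 | 7.3 | 1.2% | 4.6% | 10.4% |

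These are gains before the cost of extra strata. Simulating the Mantel-Haenszel difference over four tool x grade strata (200,000 trials per scenario) gives a cost of about 0.7% at g = 0, and net gains of about 1%, 4-7% and 10-16% at g = 10, 20 and 30. A difference standardised to the grade distribution does less well: it costs 1-3% at g = 0 and gains about 2-4% at 20 points and 8-13% at 30.

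**5. Validity and power.** In a second simulation (40,000 trials per scenario) the mean error of the crude difference was at most 0.1 point throughout. With 30% response in both arms, the tool-only CMH test rejected in 4.7-5.0% of trials. Power with 282 vs 47, tool only against tool x grade:

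- 50% vs 30%: 74.0% and 73.7% at g = 0; 73.5% and 75.1% at g = 20; 73.4% and 77.3% at g = 30.
- 60% vs 30%: already about 97.5% with tool only.
- 70% vs 30%: at least 99.9% either way.

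**The case against.** The strongest objection is that the planned test is sound and the gain speculative. Much of this stands.

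- **Bias.** A reader might infer that chance imbalance biases the result. It does not. Under randomisation the imbalance is part of sampling error, the standard error already includes it, and the test holds its level. Only a shift conditional on an observed imbalance remains.
- **Tool as stratifier.** A reader might infer that tool is meaningless for uninjected controls. The documents do not support that. Each site uses one tool (Protocol 4.1), so every control belongs to a needle or a cannula site. Tool, or site nested within it, also structures the randomisation.
- **Ignoring baseline.** Eligibility, the responder definition and the baseline table all use baseline grade. It is only not adjusted for.
- **Prognostic strength.** The documents do not give it. The entry threshold can also produce apparent improvement at grade 2, when a subject over-rated at baseline is later rated 1, and this partly offsets the ceiling argument. The 80% vs 15% case at 30 points is a boundary case, since control response would have to be 0% at grade 2 and 30% at grade 3.
- **Effect on the conclusion.** At 80% vs 15% the z-value is about 65/5.7 = 11. A 6% variance gain narrows the interval half-width only from 11.2 to 10.9 points.
- **Redaction.** Text after SAP 2.4.3, subgroup details and Appendix H are not visible, so an analysis by grade may already exist.

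What survives is that the covariate is already collected, that grade cannot be presumed non-prognostic on a scale without prior data, and that the cost of adjusting is small.

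**Conclusion.** The point holds as a minor matter of efficiency and robustness. The visible primary analysis adjusts for tool but not for baseline grade, and Protocol and SAP agree on this. The consequence is a modest loss of precision and, with about a 20% chance at 47 controls, an imbalance above 10 points that moves the estimate by roughly 1 to 4 points. The gain from adjusting is about 1% of variance at a 10-point gradient, 4-7% at 20 and 10-16% at 30. These sizes depend on the assumed response rates, gradients and 50% share severe.

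A reader might go further and conclude that the trial's significance is in doubt. The figures do not support that for a large effect. Only with a smaller effect (50% vs 30%) and a steep gradient does power change visibly. The benefit lies mainly in the estimate and its interval.

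**What to change.** Before database lock, stratify the CMH test by tool x baseline Blinded Evaluator grade, with two grade levels (both sides grade 2; at least one side grade 3). Report the Mantel-Haenszel risk difference with a stratified 95% interval, and state how both are combined across imputations. If the primary test is to stay as written, pre-specify this as the main supportive analysis. If the redacted text already does so, the sponsor need only confirm it. State also which stratum takes any mITT subject whose baseline grade was ineligible, since SAP 2.3.2 removes such subjects only from the per-protocol set.

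The cost is SAP wording and a variance loss of about 1% (at most about 3%, depending on the weights) if grade is not prognostic. Four strata leave 47/4, or about 12, randomised controls each on average, and fewer in the mITT set. Keeping all three bilateral patterns (2/2, 2/3, 3/3) would leave 47/6, or about 8, so two levels are preferable.
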